9.7.2 Safety Analysis

A Pearson's Chi-Squared test will be used to compare the incidence of complications associates with LAA exclusion between the two procedure groups. Alternatively, a Fisher's Exact test will be used if justified by small cell counts (less than 5) and Clopper-Pearson (Exact) 95% CI will also be reported. Thromboembolic and hemorrhagic events will be similarly analyzed.

In addition, complications associated with LAA exclusion and thromboembolic/hemorrhagic might also be analyzed using multiple logistic regression model similar to the effectiveness endpoint (successful LAA exclusion) described above.

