9.2 Study Endpoints

The following endpoints will be collected for this hypothesis generating pilot study:

- 1. Perioperative complications associated with AtriClip placement. [Defined as: stroke, major bleeding that requires re-operation and/or transfusion of > 2 U packed red blood cells (PRBC) within any 24-hour period during the first 2 days' post-index procedure, myocardial infarction (MI), or death.]
- 2. Intraoperative successful exclusion of LAA. [Defined as no (0 mm) flow between LAA and LA and < 5 mm LAA remnant by intraoperative TEE with Doppler.]
- 3. Composite event rates between the group of subjects diagnosed with POAF (AtriClip vs no AtriClip) through 365 days' post index procedure and between the group of subjects not diagnosed with POAF (AtriClip vs no AtriClip) through 30 days' post index procedure. Events to be evaluated include: Thromboembolic & Hemorrhagic Events such as cerebrovascular accident (CVA), transient ischemic attack (TIA), peripheral ischemia, hemorrhagic stroke, neurologic bleed, gastrointestinal (GI) bleeds, or other major bleeding event.
- 4. Composite event (listed above) rates through 365-days post index procedure for all AtriClip patients, regardless of whether the patient develops POAF.
- 5. Healthcare resource utilization variance between groups as related to the composite events above. [Specifically hospital length-of-stay (LOS), reoperation for bleeding, neurologic consults for stroke or TIA, emergency department (ED) visits, and hospital readmissions.]

[figure not shown]

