9.4 Sample Size and Power

This is a prospective, multicenter, randomized (2:1), unblinded study conducted in up to 2000 patients at risk of POAF based on the CHA2DS2-VASc and HASBLED scoring at up to 20 USA sites. All patients who undergo a valve or CABG (structural heart) procedure with direct visual access to the LAA will be eligible to participate based upon the inclusion and exclusion criteria defined in this protocol.

A total of up to 2000 patients (approx. 1333 in AtriClip group, approx. 667 in SOC group) at risk of POAF will be enrolled in this study. It is assumed that 40% of the patients will be diagnosed with POAF. A two treatment group one-sided Z-test with continuity correction and an $\alpha = 0.05$ will have 80% power to detect the difference between a medical management (SOC) safety rate of PS = 12.5% and a mechanical exclusion

Study Number: CP2015-2 CONFIDENTIAL Page 35 of 48

(AtriClip) safety rate of PC = 6.25% at 30-days post-op when the sample size (for completers) for patients diagnosed with POAF is 485 in the AtriClip group and 243 in the SOC group (a total sample size of 728). Adjusting for loss to follow-up, 533 patients in the AtriClip group and 267 in the SOC group (a total sample size of 800) are expected to be diagnosed with POAF.

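### The 365-day composite is tested only as a crude proportion, with no rule for partly followed subjects; cumulative incidence at day 365 is a cheap improvement

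*Combined protocol and SAP*

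**What the plan says.** - **Endpoint.** Section 9.2, endpoint 3: "Composite event rates between the group of subjects diagnosed with POAF (AtriClip vs no AtriClip) through 365 days" after the index procedure. Subjects without POAF are compared through 30 days. Endpoint 4 is the 365-day rate in all AtriClip patients, a single-arm figure.
- **Components.** CVA, TIA, then "peripheral ischemia, hemorrhagic stroke, neurologic bleed, gastrointestinal (GI) bleeds, or other major bleeding event". Death is not listed. It is a component only of endpoint 1, the perioperative complications, whose list ends "myocardial infarction (MI), or death".
- **Test.** Section 9.7.2: "A Pearson's Chi-Squared test will be used to compare the incidence of complications associates with LAA exclusion between the two procedure groups", with Fisher's exact test for small cells. Then: "Thromboembolic and hemorrhagic events will be similarly analyzed".
- **Optional model.** These events "might also be analyzed using multiple logistic regression model similar to the effectiveness endpoint". That model is also binary and takes no account of follow-up time.
- **Expected loss.** Section 9.4 requires 485 + 243 = 728 completers with POAF, then: "Adjusting for loss to follow-up, 533 patients in the AtriClip group and 267 in the SOC group", 800 in total. No percentage is given.
- **Exits.** Section 4.2.6 lists loss to follow-up, withdrawal and death among the reasons for early termination and does not replace withdrawals. Section 4.2.7 limits follow-up after early termination to 30 days.
- **Populations.** Section 9.6 bases safety on a modified ITT population and makes the POAF subset primary for effectiveness and health economics.

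The statistical section names no survival, cumulative-incidence, person-time, censoring, competing-risk or missing-outcome method. Section 9.8 makes a separate detailed SAP conditional on need.

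**The concern.** A one-year proportion needs each subject's status at one year. Someone who exits on day 60 and is followed for 30 more days has no known status at day 365, yet a chi-square table must put that subject in a cell or leave the subject out. Counting such subjects as event-free pulls the rate down; dropping them pushes it up, because a subject whose event came before exit stays in while event-free subjects who exit go out. If loss differs by arm, the two rules bias the comparison in opposite directions.

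The documents point both ways: the ITT definition suggests keeping these subjects, and a sample size expressed in completers suggests dropping them. In an unblinded trial with no stated rule, the choice could be made after results by arm are visible.

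**Working it through.** **1. The plan's own figure.** Inputs from section 9.4: 12.5% against 6.25%, one-sided alpha 0.05, 80% power, continuity correction, allocation 2:1. With unpooled variance:

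n(SOC) = (1.645 + 0.842)² × [0.125×0.875 + 0.0625×0.9375/2] / 0.0625² = 219.5.

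Continuity correction: (219.5/4) × [1 + √(1 + 3/(219.5×0.0625))]² = 242.9, so 243 SOC and about 485 AtriClip. The stated size is reproduced. Implied loss: 1 − 728/800 = 9.0%.

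**2. Crude 365-day rate under each rule.** Assumptions, none of them in the documents: true 365-day risk p = 0.20; half the events uniform on days 0–30 and half on days 30–365; a fraction l lost at times uniform over the year, independent of events; no deaths. Mean event time as a share of the year:

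m = (0.5×15 + 0.5×197.5)/365 = 0.291.

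- Lost counted event-free: A = p(1 − l·m).
- Lost dropped: B = A / [1 − l(1 − p) − l·p·m]. The last term removes subjects lost before an event they would later have had.

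| Loss l | A | Denominator of B | B |
|---|---|---|---|
| 5% | 19.7% | 0.957 | 20.6% |
| 9% | 19.5% | 0.923 | 21.1% |
| 15% | 19.1% | 0.871 | 22.0% |
| 20% | 18.8% | 0.828 | 22.7% |

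A simulation of 4 million subjects agrees at 9% and 20% loss.

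**3. No true effect, loss 5% in one arm and 15% in the other.**
- Event-free: 0.1971/0.1913 = 1.03, or 0.97 with the arms swapped; difference 0.6 percentage points.
- Dropped: 0.2059/0.2195 = 0.94, or 1.07 swapped; difference 1.4 points.

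**4. The same check at the plan's rates.** Assumption: 6.25% and 12.5% are used as 365-day rates, with constant hazards λ for events and μ for loss (time in years), where λ = −ln(1 − p) and μ = −ln(1 − l). The event-free rate is λ/(λ+μ) × (1 − e^−(λ+μ)); the dropped rate divides this by 1 minus the share lost before an event.
- Equal 9% loss: 5.97%/11.94% event-free, 6.54%/13.04% dropped; the ratio stays about 0.50.
- Loss 5% AtriClip, 15% SOC: ratio 0.53 event-free, 0.48 dropped.
- No effect (12.5% in both arms), 533/267, two-sided 0.05: rejection rate 5.0% with equal loss, 5.6–6.0% with 5% against 15%, 6.5–7.1% with 5% against 20%.

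**5. Bounds if loss is informative.** At 9% loss, 533 − 485 = 48 and 267 − 243 = 24 subjects are lost. Completer events at the plan's rates: 0.0625×485 = 30.3 and 0.125×243 = 30.4. If none or all of those lost have an event:
- AtriClip: 30.3/533 = 5.7% to 78.3/533 = 14.7%.
- SOC: 30.4/267 = 11.4% to 54.4/267 = 20.4%.

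The ranges overlap, so in the extreme the sign could reverse.

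**6. Does the better method cost power?** Under step 4 with 9% loss and no deaths, the cumulative-incidence variance per arm is (1−p)² × λ/(λ+μ) × (e^(λ+μ) − 1)/n: 0.000430 (SOC) and 0.000115 (AtriClip). The standard error of the difference is 0.0234, and the expected z is 0.0625/0.0234 = 2.68. The crude difference with unpooled standard error gives 0.0597/0.0223 = 2.67 event-free and 0.0650/0.0243 = 2.68 dropped. The cost is negligible.

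**The case against.** - **The bias is small.** With loss that is non-informative and similar by arm, the ratio barely moves, and 5% against 15% lifts type I error only to about 6%. This stands.
- **The 9% may not be a one-year figure.** It is back-calculated from a sample size whose rates are at 30 days. This also stands, and is why a range of loss is shown.
- **Little of the plan is exposed.** The comparison without POAF ends at day 30, and early-terminated subjects are followed for 30 days. Only the 365-day POAF comparison and the single-arm endpoint 4 rate are materially affected. In the POAF comparison both arms have the same planned follow-up (section 4.1).
- **The study is exploratory and a SAP may follow.** Section 9.7 allows further analyses as needed. But it also tests at two-sided 0.05, and section 9.8 does not guarantee a SAP. This softens the point without answering it.
- **Death.** A reader might infer that counting a patient who dies without an event as a non-event is a bias that the better method removes. It is not. Aalen-Johansen treats that patient the same way, and with complete follow-up it equals the crude proportion. An arm with more early deaths can look safer under either method; only a separate look at deaths shows it.

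**Conclusion.** The concern holds as a cheap improvement. For the one comparison that runs to a year, the plan names only binary methods, expects incomplete follow-up, and gives no rule for it. Under the assumptions in the working, the crude rate is off by 0.5 to 1.1 percentage points at 9% loss and by 1.2 to 2.7 points at 20%; a null risk ratio moves to between 0.94 and 1.07 at 5% against 15% loss. Informative loss could do more, and the documents give no means of sizing it beyond the bounds.

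A reader might also infer that the plan scores lost subjects as event-free, or that loss will differ by arm. The documents say neither. The first is one of two rules that a binary test forces; the second is possible in an unblinded trial, but no passage predicts it.

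**What to change.** Amend section 9.7.2, or write it into a SAP finalized before data are seen:

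1. Make the main 365-day analysis the Aalen-Johansen cumulative incidence at day 365, censoring at last contact, with death as a competing event. Use it for the endpoint 3 comparison in POAF subjects and for the endpoint 4 rate.
2. Compare arms in POAF subjects by the day-365 risk difference with a 95% CI.
3. Tabulate deaths and losses by arm, and report event-or-death as a sensitivity analysis, since the main method leaves the death question open.
4. Add a sensitivity analysis for informative loss.
5. Keep the chi-square or Fisher test as supportive, with its rule for partly followed subjects stated.
6. Do not stratify by individual small sites. With 267 SOC subjects with POAF, the synopsis's 40 sites give 267/40 ≈ 7 each, and section 9.4's 20 sites give about 13; at 12.5% that is roughly 0.8 or 1.7 SOC events per site.

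The cost is wording and slightly more programming. The method assumes non-informative censoring, hence item 4. It also needs the dates of every composite event. Section 10.2.4 limits adverse event reporting to the sponsor to events related to the exclusion procedure or device, so the sponsor should confirm that all composite events and their dates are captured regardless of relatedness. The chi-square needs those events too.

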4.0 INVESTIGATIONAL PLAN

4.1 Overall Study and Design – Subject Disposition Diagram

Study Number: CP2015-2 CONFIDENTIAL Page 18 of 48

Overall Study and Design - Description

All patients who undergo a valve or CABG (structural heart) procedure with direct visual access to the LAA will be eligible to participate based upon consent and evaluation of the inclusion and exclusion criteria defined in this protocol.

The target patient population includes patients at risk of POAF based on the CHA2DS2-VASc and HASBLED scoring.

Patient must meet all inclusion/exclusion criteria (including intra-operative exclusion criteria) before enrollment or randomization.

During the planned structural heart procedure, the intra-operative exclusion criteria will be assessed. If any intra-operative exclusion criteria are met, the subject will be a screen fail and will not be enrolled or randomized.

To execute randomization, at the time of enrollment, subjects will be assigned a sequential identification number at each site and a corresponding sealed envelope which will be opened in the operating room to reveal the treatment group. Subjects will be randomized 2:1 (2 with AtriClip® to 1 with no AtriClip®). Randomization sequences will be generated by the AtriCure Statistician and will be stratified by site. The subject population will be randomized using a blocking scheme for each surgeon to ensure equal and balanced treatment group allocations and to avoid bias with respect to known or unknown subject variables that could affect the outcome of this study.

Post-index procedure, all subjects will be monitored per the hospital standard of care processes for POAF.

Four (4) treatment arms result:

- Surgery with AtriClip (POAF diagnosed / Institution SoC anticoagulation therapy)
- Surgery with AtriClip (No POAF)
- Surgery with no AtriClip (POAF diagnosed / Institution SoC anticoagulation therapy)
- Surgery with no AtriClip (No POAF)

Subjects will be assessed for AEs related to the placement of the AtriClip and will be instructed to notify the PI of any AEs that occur during the study. All subjects that develop POAF during the hospital stay will be followed for approximately 1 year (365 days) post index procedure. In addition, all the subjects in the AtriClip group that do not develop POAF will also be followed for 365-days post index procedure.

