9.5 Randomization

Upon enrollment, subjects will be assigned a sequential identification number at each site and a corresponding sealed envelope which will be opened prior to the index procedure to reveal the treatment group. Subjects will be randomized 2:1 (2 with AtriClip to 1 anticoagulation therapy and without AtriClip). Randomization sequences will be generated by AtriCure Statistician using SAS version 9.4 (SAS Institute Inc., Cary, North Carolina) and will be stratified by site.

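### The committed tests for complications and the thromboembolic/hemorrhagic composite ignore the site stratification used at randomisation, and no interval for the treatment difference is specified

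*Combined protocol and SAP*

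**What the plan says.** **Allocation.** Section 9.5 says of the 2:1 randomisation sequences that they "will be stratified by site". Section 4.1 also states site stratification and adds a second layer: "The subject population will be randomized using a blocking scheme for each surgeon". Section 9.5 does not mention surgeons.

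**Tests of events.** Section 9.7.2: "A Pearson's Chi-Squared test will be used to compare the incidence of complications associates with LAA exclusion between the two procedure groups". Fisher's exact test replaces it when cells are small, and Clopper-Pearson intervals are reported. For the composite: "Thromboembolic and hemorrhagic events will be similarly analyzed". Neither test uses site.

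**Optional model.** The same section says that these endpoints "might also be analyzed using multiple logistic regression model similar to the effectiveness endpoint (successful LAA exclusion) described above". The model referred to, in section 9.7.1, lists sites or clusters of sites, surgical approach, age, gender, the two risk scores and interactions. Procedure group is not in the list.

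**Resource use.** Section 9.7.1 commits to a two-way ANOVA for length of stay, OR time and cost, with procedure group and site as fixed effects.

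**General provisions.** Section 9.7 sets two-sided testing at 0.05, promises 95% intervals where suitable, calls the study exploratory and allows covariates when needed. Section 9.8 provides for a later detailed analysis plan only if needed.

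**The concern.** An analysis should normally respect the strata within which patients were allocated. Blocked 2:1 allocation within site keeps the arms balanced on site. If sites differ in event rate, the unstratified standard error ignores that balance and is too large. Sites plausibly differ here: section 4.1 leaves POAF monitoring, and section 5.3 leaves anticoagulation, to local standard of care. POAF detection and bleeding both depend on these.

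The plan is also uneven. Length of stay and cost receive a committed site term, while the clinical events on which section 9.4 sizes the trial do not, and no reason is given.

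Finally, a hypothesis-generating study is read mainly for an effect estimate and its uncertainty. Clopper-Pearson is an interval for a single proportion, so it describes each arm and not the difference. As written, the choice between an adjusted and an unadjusted result stays open in an unblinded trial for which section 12.1 anticipates no independent oversight.

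**Working it through.** **1. Reproduce the plan's sample size (section 9.4).** Inputs: 12.5% versus 6.25% at 30 days, 2:1, one-sided 0.05, 80% power, continuity correction. With unpooled variance,

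n(SOC) = (1.645 + 0.842)² × [0.125×0.875 + 0.0625×0.9375/2] / 0.0625² = 219.5.

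With continuity correction, (219.5/4) × [1 + √(1 + 3/(219.5×0.0625))]² = 242.9, so 243. This agrees with the stated 243 + 485 = 728 POAF completers. The two-sided uncorrected chi-square test of section 9.7 has 79.8% power at 243/486, which is the baseline for what follows.

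**2. How thin the strata are.** Section 9.4 gives up to 20 sites and the synopsis up to 40.
- POAF completers per site: 728/20 = 36.4; 728/40 = 18.2.
- Expected events: 485×0.0625 + 243×0.125 = 60.7, or 8.3% overall. Per site: 60.7/20 = 3.0; 60.7/40 = 1.5.

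**3. What site stratification does.** The comparison is Pearson chi-square against site-stratified Cochran-Mantel-Haenszel (CMH), by simulation, two-sided 0.05, 20 or 40 sites, no pooling. The documents give no between-site variance, so the logit SD is an assumption, taken from 0 to 1.2.

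Blocks apply to everyone randomised, whereas POAF is diagnosed afterwards. The POAF subset must therefore be drawn from the randomised subjects: 728/0.40 = 1,820 completers, of whom 40% then develop POAF. Equal-sized sites and POAF arising at random are further assumptions.

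*POAF subset, 12.5% versus 6.25%, 20,000 trials per setting. Power of CMH minus chi-square, percentage points:*

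| Logit SD | 20 sites | 40 sites |
|---|---|---|
| 0 | -0.8 | -1.5 |
| 0.5 | 0.0 | -1.0 |
| 0.8 | +0.9 | +0.3 |
| 1.2 | +3.0 | +2.4 |

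Chi-square type I error was 4.8% to 5.1% at SD 0.5 to 0.8. At SD 1.2 it was 4.2% (20 sites) and 4.7% (40 sites). Other runs of the same design gave differences from -1.6 to +2.8 points, so about -1.5 to +3 is a fair summary.

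*All randomised subjects (as for endpoint 1; 12.5% versus 8.5% assumed for illustration).* The difference ran from about 0 to +3.5 or +4 points. At SD 1.2 chi-square type I error was 3.6% to 4.0%, against 4.9% to 5.3% for CMH.

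**4. Why the two populations differ.** Among all randomised subjects the 2:1 balance within site holds, so stratifying removes between-site variation at almost no cost. In the POAF subset that balance is only partly kept, so the chi-square test is closer to nominal. Sparse sites with uneven arms carry little information for CMH, which therefore loses slightly when there is little site variation to remove.

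**5. How extreme is SD 1.2?** Around 8.3%, logit = -2.40; -2.40 ± 1.96×1.2 gives -4.75 and -0.05. So 95% of sites would have rates between about 0.9% and 49%. At SD 0.5, -2.40 ± 0.98 gives about 3% to 19%. The larger gains need very large site differences.

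**The case against.** The strongest reply is that nothing is invalid. A reader might infer that ignoring the stratification produces false positives. It does not: in every setting above, the chi-square type I error is near or below 5%. Preferring CMH is then a matter of efficiency in a study that calls itself exploratory. This stands, and it limits the weight of the point.

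A reader might also infer that the plan makes no provision for site adjustment. It does: these endpoints "might also be analyzed using multiple logistic regression model", and site is among that model's terms. But the model is optional and lists no treatment term, so as written it defines no adjusted treatment effect.

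Nor can it be said that the plan offers no confidence intervals. Section 9.7 promises 95% intervals where suitable. The supportable criticism is narrower: none is specified for the treatment difference.

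Stratifying is not a free gain either. In the POAF subset, with 40 unpooled and similar sites, CMH loses up to about 1.5 points of power. Pooling limits this, at the price of weaker stratification.

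Last, the stratum is not fully clear, because section 4.1 has blocks per surgeon as well as strata by site. A site-stratified test follows the one factor that both sections name, but it does not reflect surgeon blocks.

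**Conclusion.** The point holds as an improvement, not as an error that threatens validity. Randomisation is stratified by site; the only committed tests for complications and the composite are not; the model that could adjust for site is optional and lists no treatment term; and no interval for the treatment difference is specified.

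The effect on power is modest: about 0 to +4 points with all randomised subjects, and about -1.5 to +3 points in the POAF subset. Both ranges rest on an assumed between-site logit SD of 0 to 1.2, equal-sized sites, POAF arising at random, and 20 or 40 unpooled sites. The upper ends need site differences that may well not occur.

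The case for the missing risk difference and interval rests on no simulation, and is the firmer reason to act.

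**What to change.** In section 9.7.2, or in the detailed plan foreseen in section 9.8:

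- For endpoints 1 and 3, name the site-stratified CMH test as the planned test, with the Mantel-Haenszel common risk difference and its 95% confidence interval.
- Fix a rule for pooling small sites before database lock, for example a minimum number of subjects per stratum. At roughly 18 to 36 POAF completers and 1.5 to 3 events per site, this is needed.
- Keep Pearson/Fisher and the per-arm Clopper-Pearson intervals as supportive.
- If the logistic model is kept, list procedure group among its terms.
- Reconcile sections 4.1 and 9.5 on whether blocks are by site or by surgeon, so that the analysis stratum is unambiguous.

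This costs a few lines of text and no new data, since allocation is already by site. The downside is up to about 1.5 points of power in the POAF subset if sites are many, unpooled and similar, which the pooling rule limits.
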